**Figure 5 Expectedness Classification of Adverse Events**

Abbreviations: AE = adverse event; eCRF = electronic Case Report Form.

#### 9.3.1 Expected Adverse Events

##### 9.3.1.1 Captured Expected Adverse Events

The following expected AEs may occur at any time in the course of managing diabetes. Immediate or short-term risks to subjects from some of these expected AEs are higher than those identified under Non-Captured Expected AEs.

Therefore, for the purposes of this study, the following expected AEs will be considered captured expected AEs and the AE Form in the eCRF needs to be completed:

- Symptomatic hypoglycemia episodes (see Section 9.2.2).

- Hyperglycemia in combination with medical intervention.
- Hyperglycemia in combination with medical intervention or suspected by the site staff to be caused by insulin leakage or infusion set occlusion.
- Infusion site infection and abscesses, if applicable.
- Unintentional needle stick injury with the guiding needle of the infusion set, if applicable.
- Plaster reactions to the infusion set, if applicable.
- Generalized hypersensitivity reactions.
- Ketosis and ketoacidosis.

These captured expected AEs will be handled as follows:

Subjects will be instructed to follow their personal physicians' instructions for management of low and high blood glucose values or otherwise as instructed by the Investigator.

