### **9.2.4 Hyperglycemic Episode**

Hyperglycemia is defined as high blood glucose readings, a recommended threshold to intervene could be defined as values above 250 mg/dL (13.9 mmol/L). However, investigators should consider the condition of the individual subject.

Only hyperglycemia episodes in combination with medical intervention or additional diagnostic procedures have to be documented as AE in the eCRF, as described in Section 9.3.1.1.

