### **9.3.1.2 Non-Captured Expected Adverse Events**

Non-Captured expected AEs may occur at any time in the normal course of managing diabetes. For the purpose of this study, they will be considered as non-captured expected AEs and will not be documented in the eCRF, these include:

- Asymptomatic hypoglycemia episode (see Section 9.2.1).
- Hyperglycemia without medical intervention.
- Hyperglycemia with a suspected cause other than infusion set leakage or occlusion and without medical intervention.
- In the event of a sore finger, subjects will be advised to avoid taking self-monitoring blood glucose samples from that finger.
- In the event of a mild infection at a lancing site, the study subject will be reminded to wash hands before all blood tests and encouraged to consult their nurse or physician on the management of an infection.
- Minor skin damage due to plaster removal which disappears within a few hours.
- Minor bleeding into the infusion set plaster or into the catheter or tubing, if applicable.
- Mild discomfort by plaster or cannula that may result into replacement decision by the subject.
- Also, both planned ambulant contacts and planned hospitalizations for training purposes will be considered non-captured adverse events.

Since these non-captured expected Adverse Events identified above are common as well as expected and pose minimal immediate risk to the subjects, they will not be tracked and logged as AEs during the course of the study. Investigators may log reports of these non-captured expected AEs as is customary within their practice.

These non-captured expected AEs will be handled as follows:

Subjects will be instructed to follow their personal physicians' instructions for management of low and high blood glucose values as well as for minor skin damage, minor bleeding and mild discomfort.

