## 2.4. Treatment Groups

**Group A:** Continuous subcutaneous insulin infusion (CSII) with the Accu-Chek® Solo micropump system for 39 weeks (26+13).

**Group B:** Multiple daily injections (MDI) for 26 weeks plus 13 weeks with the Accu-Chek® Solo micropump system.

**Group C:** Continuous subcutaneous insulin infusion (CSII) with the mylife™ OmniPod® therapy system for 26 weeks plus 13 weeks with the Accu-Chek® Solo micropump system.

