### 6.9. Therapy Parameters

The following event frequencies will be listed for each individual subject and will also be tabulated by treatment group and visit. Additionally, event frequency differences between V4 and V5 will be tabulated. Tabulations will be performed both based on the number of affected subjects and on the total wear time of the three study devices during the analyzed period.

- Hyperglycemia and related events (e.g., Ketosis or Ketoacidosis) likely caused by insulin underdosing
- Hypoglycemia
- Hospitalizations

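### Three protocol sections give incompatible rules for recording hyperglycaemia without medical intervention, so AE-based counts may vary by site and, in part, between MDI and the pump arms

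*Protocol*

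**What the plan says.** Three sections of the protocol decide which hyperglycaemia episodes become AE records.

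- **9.2.4:** "Only hyperglycemia episodes in combination with medical intervention or additional diagnostic procedures have to be documented as AE in the eCRF". It refers the reader to 9.3.1.1.
- **9.3.1.1** lists two captured categories: first "Hyperglycemia in combination with medical intervention", then "Hyperglycemia in combination with medical intervention or suspected by the site staff to be caused by insulin leakage or infusion set occlusion". Additional diagnostics are not mentioned.
- **9.3.1.2** lists expected events that "will not be documented in the eCRF, these include" two hyperglycaemia categories: first "Hyperglycemia without medical intervention", then "Hyperglycemia with a suspected cause other than infusion set leakage or occlusion and without medical intervention".

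On the analysis side, the frequency of hyperglycaemia is a secondary parameter (Protocol 4.2 and 11.6). SAP 6.9 tabulates "Hyperglycemia and related events (e.g., Ketosis or Ketoacidosis) likely caused by insulin underdosing" by treatment group and visit, both by affected subjects and by device wear time, with a Visit 4 to Visit 5 difference. It names no data source. SAP 6.12 summarises AEs per year of device use and gives adverse device effect (ADE) rates per 100 patient-years.

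**The concern.** A site that meets a suspected occlusion, corrected without medical intervention, is told in one place to complete the AE form and in another not to document the episode. A site that ran additional diagnostics, but did not intervene, has the same difficulty with a different pair of sections. Two careful sites can therefore produce different counts from the same events.

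The disagreement also touches the treatment comparison. Suspected leakage or infusion set occlusion is, in practice, a route to capture for pump users only. Arm B receives "Multiple daily injections (MDI) for 26 weeks plus 13 weeks with the Accu-Chek® Solo micropump system", so its subjects gain that route at Visit 4. If the route is used, part of the change from Visit 4 to Visit 5 reflects a change in what is recorded. If it is not used, such episodes on a device without CE marking at study start may never be logged as AEs. Protocol 9.1.3 counts events resulting from malfunction as ADEs, so the ADE rates could then be too low.

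**Working it through.** **1. The rules side by side.** Classify an episode by medical intervention (I), additional diagnostics (D) and suspected leakage or occlusion (L).

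| Episode | 9.2.4 | 9.3.1.1 | 9.3.1.2 | Consistent? | Possible in which arms |
|---|---|---|---|---|---|
| I | record | record | not excluded | yes | all |
| L only | not recorded | record (second category) | excluded by first category, spared by second | **no** | pump arms, in practice |
| D only | record | not listed | excluded | **no** | all |
| D and L, no I | record | record | excluded by first category, spared by second | **no** | pump arms, in practice |
| none of I, D, L | not recorded | not listed | excluded | yes | all |

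Episodes with intervention, and episodes with none of the three features, are handled the same way throughout. The conflict is confined to L and D without intervention. Section 9.3.1.2 also disagrees with itself, because its first category removes the exception that its second implies.

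**2. Is there another event source?** Protocol 9.2 sends episodes to a subject diary where there is one, or to the visit descriptions. Section 7.11 says there is no study diary. The visit descriptions in 7.3 to 7.6 and the schedule of assessments ask about hypoglycaemic events, not hyperglycaemia. The AE form therefore appears to be the only source of hyperglycaemia events. SAP 6.9 groups hyperglycaemia with ketosis and ketoacidosis, and SAP 3.5.5 allows differently coded terms with a common cause, such as lack of insulin, to be pooled. Both fit an AE-based count, although the SAP does not say so.

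**3. Which outputs are exposed?**
- Exposed: hyperglycaemia rows in SAP 6.9 and the AE and ADE summaries in SAP 6.12.
- Not exposed: the fractions of meter and CGM readings by glucose range in SAP 6.8.4, which come from glucose data, and the DTQ analysis in SAP 6.6.
- Solo versus OmniPod: both arms have the leakage/occlusion route, so it does not favour either.

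**4. Size.** The documents give no hyperglycaemia rate, so only the form of the effect can be shown. Assume:
- rate r of intervention episodes, equal in Solo and MDI;
- leakage/occlusion-only episodes on Solo at rate k × r, and none on MDI;
- planned exposure of 60 × 26/52 = 30 patient-years per arm, without dropout.

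Expected counts where L is recorded: MDI 30r, Solo 30(r + kr). The ratio is 30r(1 + k)/30r = 1 + k, and the exposure cancels.

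| k (assumed) | Ratio if L is recorded | Ratio if only I is recorded |
|---|---|---|
| 0.25 | 1.25 | 1.0 |
| 0.5 | 1.5 | 1.0 |
| 1 | 2.0 | 1.0 |
| 2 | 3.0 | 1.0 |

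If a share p of each arm's exposure is at sites that record L, the ratio is 1 + p × k. With k = 1 and p = 0.5 it is 1 + 0.5 × 1 = 1.5. The same events can thus give any ratio from 1 to 1 + k, depending on how sites read the protocol. The values of k and p are illustrations, not estimates.

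**The case against.** The strongest reply is that a workable reading exists. The second categories in 9.3.1.1 and 9.3.1.2 are complements: intervention or leakage/occlusion is captured, and other causes without intervention are not. Section 9.2.4 itself points to 9.3.1.1. On that reading the rest is untidy drafting, and variation between sites is conjecture. This stands in part: it may be what was intended, and the documents do not show what sites did. But it requires the site to ignore the first exclusion in 9.3.1.2 and the diagnostics criterion in 9.2.4, and nothing tells it to. Section 9.3.1.2 also lets investigators log non-captured events according to their own practice.

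Second, pump leakage and occlusion are real hazards, and their near absence under MDI is largely genuine. This stands. A reader might infer that any rise in arm B after the switch to Solo would be an artefact. The documents do not support that, since part of it would be a true device effect. What remains is that comparable MDI episodes without intervention, for example after a missed injection, have no corresponding cause-based route. The recorded difference then mixes hazard with ascertainment.

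Third, SAP 6.9 already limits its row to events attributed to too little insulin. That can occur in every arm, but the limit applies after recording and does not equalise it. Leakage and occlusion episodes would plausibly pass it.

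Fourth, device failures have other recording routes. Malfunctions are recorded at Visits 3, 4 and 5 (Protocol 7.4 to 7.6), SAP 6.12 tabulates defective devices, and 9.3.1.1 captures ketosis and ketoacidosis whether or not there was intervention. This stands: the risk is that the glucose episode is missing from the AE tables, not that the device failure leaves no trace.

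**Conclusion.** The three sections cannot all be followed for suspected leakage or occlusion without intervention, or for additional diagnostics without intervention. AE-based hyperglycaemia and ADE counts may therefore depend on which section a site applied. Where the leakage/occlusion criterion is used, the Solo versus MDI comparison and arm B's Visit 4 to Visit 5 difference may mix device effect with a difference in capture.

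A reader might infer that the widest rule can be met only by pump users, and that hyperglycaemia is therefore not comparable between Solo and MDI. The documents do not support this. MDI subjects can meet the rule in 9.3.1.1 through medical intervention, and only the added limb is specific to pumps. No single rule is widest, because 9.2.4 goes further on diagnostics, which any arm can meet. Capture limited to intervention treats all arms alike, and the glucose-range fractions remain comparable as far as this issue goes.

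The consequence is limited. SAP 6.9 specifies no test, and SAP 6.1 allows none unless specified, so the output is descriptive. The extra pump episodes would count against Solo. No event rate can be attached to the problem. The conclusion assumes that SAP 6.9 draws on AE records, which is the likely reading but is not stated. The point should be corrected, but it does not threaten the primary result.

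**What to change.** 1. Reconcile Protocol 9.2.4, 9.3.1.1 and 9.3.1.2 into one recording rule. Which rule is for the sponsor to decide.
2. Record the reason for capture on the AE form: medical intervention, additional diagnostics, suspected leakage or occlusion.
3. State the data source for the hyperglycaemia row in SAP 6.9.
4. In SAP 6.9 and 6.12, show the total and split it into episodes that meet a criterion open to all arms and episodes captured only through suspected leakage or occlusion. Use the former for the comparison with MDI and for arm B's Visit 4 to Visit 5 difference. Keep the pump-only line visible as a device hazard, so that the split does not hide it.

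The cost is one extra field, one extra table line and a somewhat smaller count for the between-arm comparison. The split cannot recover episodes that a site has already left unlogged. If any data were collected under the unreconciled text, the report should say so.

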### **9.3.1.2 Non-Captured Expected Adverse Events**

Non-Captured expected AEs may occur at any time in the normal course of managing diabetes. For the purpose of this study, they will be considered as non-captured expected AEs and will not be documented in the eCRF, these include:

- Asymptomatic hypoglycemia episode (see Section 9.2.1).
- Hyperglycemia without medical intervention.
- Hyperglycemia with a suspected cause other than infusion set leakage or occlusion and without medical intervention.
- In the event of a sore finger, subjects will be advised to avoid taking self-monitoring blood glucose samples from that finger.
- In the event of a mild infection at a lancing site, the study subject will be reminded to wash hands before all blood tests and encouraged to consult their nurse or physician on the management of an infection.
- Minor skin damage due to plaster removal which disappears within a few hours.
- Minor bleeding into the infusion set plaster or into the catheter or tubing, if applicable.
- Mild discomfort by plaster or cannula that may result into replacement decision by the subject.
- Also, both planned ambulant contacts and planned hospitalizations for training purposes will be considered non-captured adverse events.

Since these non-captured expected Adverse Events identified above are common as well as expected and pose minimal immediate risk to the subjects, they will not be tracked and logged as AEs during the course of the study. Investigators may log reports of these non-captured expected AEs as is customary within their practice.

These non-captured expected AEs will be handled as follows:

Subjects will be instructed to follow their personal physicians' instructions for management of low and high blood glucose values as well as for minor skin damage, minor bleeding and mild discomfort.

### **9.3.2 Unexpected Adverse Events**

All AEs which do not meet the criteria mentioned under expected AEs (Section 9.3.1) are considered as unexpected AEs and will be documented in an AE Form in the eCRF.

## **9.4 Assessment of Causality in Relationship to Device**

### **9.4.1 Related**

An AE is deemed related with a device if **ALL** of the following criteria apply:

- There is a reasonable temporal sequence between AE and use of the device.
- It follows a known or expected response pattern of the device.
- It cannot be reasonably explained by the known characteristics of subject's clinical state.

Adverse events resulting from insufficiencies and/or inadequacies in the instructions for use or the deployment of the device will be classified as related.

Adverse events resulting from a user error will be classified as related.

### **9.4.2 Possibly Related**

An AE is deemed possibly related if:

- There is a reasonable temporal relationship between the AE and use of the device; and
- It follows a known or expected response pattern of the device but could have been easily produced by a number of other etiologies.

### **9.4.3 Unrelated**

When there is no reasonable temporal association between the device and the AE or the event was related to the subject's clinical state or concomitant treatment(s).

### **9.4.4 Not Assessable**

When there is not sufficient information to assess a relationship.

## **9.5 Period of Observation**

All AEs ongoing at the time of study termination - irrespective their severity - should be followed up - via telephone - for a maximum of 5 days after the subject's last visit to the site. A medical statement should be included in the AE Form in the eCRF for all ongoing AEs after the Period of Observation.

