### **6.3 Point of Enrolment and Withdrawal**

A subject is considered enrolled in the study:

- as soon as he/she has signed the Subject Informed Consent Form and has been deemed eligible according to above inclusion/exclusion criteria.

A subject is considered withdrawn if he/she was first enrolled, and thereafter one or more of the following occurs:

- Withdrawal of consent to participate in the study.
- Non-compliance with the protocol procedures e.g., subject missed two consecutive study visits and/or one period with the study device(s).
- Subject requires chronic steroid in adrenal suppressive doses, other immuno-modulatory medication or chemotherapy being determined after having been enrolled.
- Subject becomes pregnant (self-reported).
- Investigator determines it is not in the best interest of the subject to continue participation in the study.

If any of the above occurs, the Investigator will:

- Ask the subject to present at site in order to ensure complete documentation (eCRF and electronic questionnaires), and to return all study materials.
- Complete the Study Completion Form in the eCRF including the date of and reason for early discontinuation.

If withdrawal occurs after completion of visit 2:

- Ask the subject to perform visit 5 as early termination visit

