### **9.1.2 Serious Adverse Event**

A Serious Adverse Event (SAE) is any AE that fulfils at least one of the following criteria:

- Led to death.
- Led to a serious deterioration in the health of a subject resulting in:
  - A life-threatening illness or injury, or
  - A permanent impairment of a body structure or a body function, or
  - An in-patient or prolonged hospitalization, or
  - A medical or surgical intervention to prevent life-threatening illness or injury or permanent impairment to a body structure or a body function.
- Fetal distress, fetal death or a congenital abnormality or birth defect.

A planned hospitalization for a pre-existing condition, or a procedure required by the study procedure, without serious deterioration in health, is not considered an SAE.

Applicable for Germany only:

Serious Adverse Event (SAE) definition according to MPSV:

A serious adverse event is defined by German Ordinance on the Medical Device Safety Plan (MPSV) as any untoward medical event in a clinical trial or performance evaluation, which is subject to approval, that directly or indirectly led, could have led or could lead to death, or resulted, could have resulted or could result in a serious deterioration of health status or death of a subject, user or another person, whether or not related to the investigational medical device.

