## 9.7 Sponsor's Responsibility to Report Serious Adverse Events/Serious Adverse Device Effects

The below **Study Safety Officer** is responsible for all safety related topics of the study:

Name:

[REDACTED]

E-mail:

[REDACTED]

Phone:

[REDACTED]

Fax:

[REDACTED]

Upon receipt of an SAE Report Form, the Study Safety Officer will:

- Review the SAE Report Form for completeness and make a medical assessment.
- Ensure that additional (initially, follow-up and final) information is obtained and communicated, as applicable.

After Safety Assessment the SAE/SADE is reported, as applicable, via the following internal lines:

Roche Q-Function is responsible for reporting of initial, follow-up and final SAE reports to:

- Regulatory Authorities.

Study Manager or designee is responsible for reporting to:

- Ethics Committees
- Other Investigators

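### Protocol 9.5 ends follow-up of every ongoing AE, SAEs included, 5 days after the last visit; this conflicts with the final SAE information required in 9.6/9.7, and no pregnancy follow-up is described

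*Protocol*

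**What the plan says.** **Cap on follow-up.** Protocol 9.5 covers every AE still open at study termination; these, "irrespective their severity - should be followed up - via telephone - for a maximum of 5 days after the subject's last visit to the site". For events still open after that it adds: "A medical statement should be included in the AE Form in the eCRF for all ongoing AEs after the Period of Observation". Section 7.7 places one call 2 to 5 days after Visit 5 when AEs or SAEs are ongoing. Footnote 1 of the Schedule of Assessments (repeated in SAP 3.3) makes the call conditional on an ongoing A(D)E or SA(D)E.

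**SAE duties.** Protocol 9.6 asks the investigator to follow up when SAE information is unsatisfactory and essential data are missing. Protocol 9.7 gives the Study Safety Officer this duty: "Ensure that additional (initially, follow-up and final) information is obtained and communicated, as applicable". It also foresees initial, follow-up and final SAE reports to the authorities. Neither section states a time limit or refers to 9.5.

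**Pregnancy.** Protocol 6.3 lists a self-reported pregnancy as a reason for withdrawal. If withdrawal comes after Visit 2, the subject is asked to attend Visit 5 as an early termination visit. Protocol 9.1.2 includes among the SAE criteria: "Fetal distress, fetal death or a congenital abnormality or birth defect".

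**The concern.** The same event falls under two instructions. For an SAE unresolved on day 5, one section sets a maximum and the next sets an open-ended duty to obtain final information. Sites could resolve this differently, and those that follow the explicit number would stop.

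The events at stake are those open at the last visit: SAEs near the scheduled Visit 5, and SAEs that led to withdrawal and are therefore open at the early termination visit. Accu-Chek Solo has no CE mark at study start (Protocol 3.3). Severe hypoglycemia and diabetic ketoacidosis are defined as SAEs (9.2.3, 9.2.5) and summarised in both documents. All remaining subjects use Solo from Visit 4 to Visit 5, so an SAE that begins in that phase arises on the investigational device.

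The pregnancy gap is a separate matter. The protocol names fetal outcomes as SAEs and foresees pregnancy during the study, but gives no step by which such an outcome would become known after withdrawal.

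**Working it through.** The check is mainly a comparison of texts, with some calendar arithmetic.

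**1. Does the cap reach SAEs?** Protocol 9.1.2 begins: "A Serious Adverse Event (SAE) is any AE that fulfils at least one of the following criteria". Every SAE is therefore an AE, and a rule for all ongoing AEs includes SAEs. The word severity in 9.5 does not mean seriousness, so the argument does not rest on it; it rests on the scope being all AEs. Section 7.7 and the Schedule footnote confirm this by naming serious events in the 2-to-5-day call.

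**2. When does follow-up end?**
- Visit 5 at week 39: 39 × 7 = day 273.
- Call window: 273 + 2 = day 275 to 273 + 5 = day 278; 278 / 7 = week 39.7. This agrees with the stated 40-week duration, so the 5-day figure is consistent with the rest of the schedule.
- With the ±14-day window on Visit 5, the limit falls between (273 − 14 + 5) / 7 = week 37.7 and (273 + 14 + 5) / 7 = week 41.7.
- For a withdrawn subject who attends early termination, the limit is that visit plus 5 days, whenever it occurs.

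**3. The instructions side by side, for an SAE unresolved on day 5**

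| Section | Instruction | Time limit |
|---|---|---|
| 9.5 | Telephone follow-up, then a medical statement | 5 days maximum |
| 7.7 | One call, SAEs named | 2 to 5 days after Visit 5 |
| 9.6 | Follow-up actions if essential SAE data are missing | None |
| 9.7 | Follow-up and final information; final report to authorities | None |

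The first two rows stop follow-up; the last two may require it to continue. No section gives either pair precedence.

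**4. Which planned outputs could change?** Protocol 11.7 and SAP 6.12 plan a listing of deaths and tables of AEs by maximum severity and by strongest causality. An event that worsens or becomes fatal after day 5 could be shown differently depending on which instruction the site followed. Event counts and rates would not change, because the event is already recorded.

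**5. Pregnancy.** Section 6.3 leads to withdrawal and, after Visit 2, an early termination visit. The call in 7.7 depends on an ongoing AE or SAE, and pregnancy is not defined as either, so even that call may not take place. Gestational timing is not in the documents. Assuming birth at 40 weeks, a report at gestational week 5 to 20 and an early termination visit soon after, (40 − 20) × 7 = 140 to (40 − 5) × 7 = 245 days remain to term. Of these, 135 to 240 days lie after day 5. This shows only that birth outcomes fall outside any described contact; fetal death can occur earlier.

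**The case against.** The strongest reply is that 9.5 is a general rule for AEs, while 9.6 and 9.7 are specific to SAEs and have no end date, so the specific duties can be read as continuing after the call. This stands in part. A reader might infer from 9.5 that final SAE outcomes cannot be collected at all. The documents do not support that: a diligent site has a basis in 9.6 and 9.7 for continuing, and 9.5 itself requires a medical statement for open events. But the protocol never says that 9.6 and 9.7 prevail, and 7.7 applies the same short window to SAEs by name. A medical statement on an unresolved event is also not its final outcome.

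A reader might also infer that 9.5 cuts off pregnancies. It does not mention them. That gap comes from silence in 6.3, 7.7 and 9.1.2, and an investigator who learned of a fetal outcome could still report it under 9.6.

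Three further points limit the weight. Pregnancy and planned pregnancy are exclusions (6.2), so few cases are likely among 180 subjects. Safety is not a primary endpoint (2.2), and most planned safety tables count events rather than outcomes. No planned table has a fetal category whose emptiness could be mistaken for absence of harm. These points reduce the size of the problem but do not remove the conflict.

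**Conclusion.** The point holds as a conflict between sections and, separately, an omission. Sections 9.5 and 7.7 cap follow-up of all ongoing AEs, SAEs included, at 5 days, while 9.6 and 9.7 require follow-up and final SAE information without limit. A site that obeys the cap would leave an unresolved SAE with a medical statement only. Independently, no procedure is described for learning the outcome of a pregnancy after withdrawal, although fetal outcomes are SAEs.

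The number of affected events cannot be estimated from the documents and is probably small. The effect is confined to safety information: final SAE outcomes, and possibly the deaths listing and the maximum-severity and causality tables. The DTQ analysis is unaffected. The conflict rests on the text alone; only the 135-to-240-day illustration depends on assumed gestational timing. It is worth correcting because the device starts without a CE mark and the correction is cheap.

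**What to change.** 1. In 9.5 and 7.7, limit the 5-day maximum to non-serious AEs.
2. State that SAEs and SADEs ongoing at the last or early termination visit are followed for information until the final report required by 9.7, with a cross-reference between 9.5, 9.6 and 9.7.
3. Add to 6.3 or 9.5 that the outcome of a pregnancy reported during the study is requested and, if it meets 9.1.2, reported on the SAE form.

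The sponsor sets the end point of follow-up. The change concerns collection of information only, not treatment.

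The cost is an amendment to protocol and consent wording and some later contacts for a few subjects. For a pregnancy those contacts may fall months after withdrawal. The sponsor should also state how information that arrives after database lock is recorded, since the documents do not describe this.
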